4 SELECTION AND ENROLLMENT OF PARTICIPANTS

Participants (N=222) in this trial must be postmenopausal women with symptomatic pelvic organ prolapse (POP). Eligible patients must be suitably healthy to undergo elective, major surgery. To be considered post-menopausal, women will need at least one year without menses or be surgically menopausal (i.e. status-post bilateral oophorectomy). Anticipated age range of participants will be from 48 years (the minimum allowed) to mid 70s, although there is not a strict age limit. Complete inclusion and exclusion criteria are summarized below.

4.1 Inclusion Criteria

- Postmenopausal, meeting criteria a, b, c, or d:
 - a. Still with uterus and no menses for >1 year

- b. Status-post bilateral oophorectomy (i.e., surgically menopausal)
 - c. Status-post hysterectomy (with or without oophorectomy) and >55 years
 - d. Vaginal pH ≥ 5 if ≤ 55 years and status-post hysterectomy but still with one or both ovaries
- Minimum age: 48 years
 - Symptomatic apical and/or anterior vaginal wall prolapse, stage 2 or greater
 - No estrogen or progesterone replacement within the last month (may come off current treatment, i.e. wash out, to join the study)
 - Medically fit for elective surgery
 - Physically able to apply/insert the study drug
 - Available for clinic follow-up for minimum 1 year

4.2 Exclusion Criteria

- Concurrent use of steroid creams for other indications (e.g. lichen sclerosis)
- BMI >35 kg/m²
- Recent history (within last month) of vaginal infection or vaginitis
- Contraindications to estrogen therapy (e.g. spontaneous DVT, stroke, breast or endometrial/ hormone-responsive cancer, genital bleeding of unknown cause)
- History of connective tissue disease
- Any estrogen, progesterone, SERM, or other medication impacting vaginal milieu, by any route (oral, transdermal, subdermal/ implantable, intravaginal, intrauterine); may come off current treatment (>1 month), i.e. wash out, to join the study
- History of vaginal irradiation
- Allergy to Premarin® or its constituents
- Prior apical repair or use of mesh for prolapse repair
- Current tobacco use

4.3 Study Enrollment Procedures

Experience from past clinical trials at each of the participating sites is that recruitment generally has not required special advertisements or alterations in existing referral patterns. Eligible patients undergo examination and evaluation for treatment in specialty urogynecology (rather than general gynecology) clinics at each site: UT Southwestern (UTSW), University of Alabama at Birmingham (UAB), and Brown University/ Women and Infants Hospital (WIH) of Providence, RI. The Research Coordinator nurse will review chief complaints and referral notes of new/ referred patients to screen for eligible study participation. A Screening Log will be maintained by the Research Coordinator or PI at each site to document identification of subjects who enter pretrial screening and reasons for ineligibility and for non-participation of eligible candidates. Weekly team research meetings also serve to remind clinic providers (residents, fellows, nurse practitioners, and faculty) of inclusion/exclusion criteria and to screen for eligible patients that may benefit from this trial.

Involvement of vulnerable populations: Fetuses, neonates, pregnant women, children, prisoners, and institutionalized individuals are not involved in this research protocol.

Consent procedure: After confirmation of study eligibility, potential subjects will be approached by the Research Coordinator, PI, or other study personnel (Co-Investigators) to describe the study in detail and obtain an informed consent from the patient. Patients will be afforded ample time to ask questions and may even take home study literature for review to return later for consent and completion of “Baseline” study evaluations. Each participating clinical site has access to in-person and telephone (i.e. “Language Line”) interpreter services should patients benefit from/ prefer study description in a language other than English. A witness will be required to co-sign the consent form.

Assigning a Subject ID: After informed consent is obtained, the Research Coordinator will assign each participant a 6-digit Subject ID number. The first 2 digits identify the clinical site, e.g. “01” for UTSW, followed by the number unique to the participant, encountered consecutively; thus, patient #1 at UTSW would receive the Subject ID 010001. Patient #7 at UAB may be 020007.

Randomization: The Data Coordinating Center (DCC) of the primary site (UTSW) will generate stratified randomization lists. Patients will be stratified by site, hysterectomy status, and duration since menopause (<10 & ≥10 years). The randomization lists with randomization codes will be distributed to each site’s research pharmacy. After informed consent is obtained, the Research Coordinator will alert the research pharmacy, and the pharmacist will assign and record the participant’s unique Randomization Code. He/she then dispenses the appropriate study cream (active CE cream vs. placebo cream). Those conducting the primary and secondary measurements as well as the patients will be blinded to treatment assignment. These data will *not* be housed in the study’s database (i.e., REDCap®). For medical reasons, there will be a protocol for breaking this blinding for providers needing to understand the medication that the patient is receiving.

5 STUDY INTERVENTIONS

5.1 Interventions, Administration, and Duration

Drug administration and dosing schedule: CE cream application dose and frequency will follow typical recommendations and the protocols observed in other clinical trials of CE cream, i.e. 1g applied vaginally nightly for 2 weeks followed by twice-weekly application. The research pharmacy at each site will house and dispense study medication. At Baseline, Surgery, and 6-mo postoperatively (i.e., Tubes #1, #2, and #4, respectively), the study cream will be dispensed directly to the patient (via Research Coordinator). At 3- and 9-mo postoperatively (Tubes #3 and #5, respectively), the study cream will be sent by the Research Coordinator to the participant via FedEx (or similar) once dispensed by the pharmacist.

Dose adjustments or escalation, changes in formulation: not applicable

Potential adverse effects:

Premarin® vaginal estrogen cream may cause some, all, or none of the side-effects listed below.

Minor side effects: vaginal itching (2-3%), breast tenderness (2-3%), vaginal discharge (6-11%)*, joint aches (7-9%)*, headache (10-13%)*.

Severe side effects: stroke (<1%), blood clots in the legs or lungs (<1%)

* = in clinical studies, the rates of these side-effects were comparable in patients treated with estrogen and placebo vaginal creams.

5.2 Handling of Study Interventions

Pfizer, Inc has agreed to provide active CE cream (Premarin® vaginal cream, PVC) for the study. A separate, central pharmacy has been identified that is able to produce *placebo cream* and receive/procure the CE cream from Pfizer. Pfizer will provide identical tubes to the PVC for the placebo cream; all tubes will be over-labeled with an opaque label to mask active vs. placebo cream. This central pharmacy, *Particle Sciences, Inc. (PSI)*, was established in 1991 as a Contract and Research Development company. It has extensive experience in pharmaceutical formulation development and characterization, especially in the area of nanoparticle suspensions and emulsions. It has substantial prior experience in production and stability testing of complex formulations—including hormone creams—under good manufacturing practices (cGMPs).

Placebo development: PSI guarantees development of placebo cream that is comparable in appearance, pH, and viscosity to the active study cream and test it for stability in batches at 0, 3, and 6 months, including under conditions designed to simulate 2-year stability, i.e. “accelerated stability” testing at 40°C and 75% relative humidity (in addition to standard testing at 25°C and 60% relative humidity). PSI is then able to provide the appropriate oversight and quality assessments of placebo cream manufacture once a satisfactory recipe is generated.

Study drug distribution & storage: PSI will coordinate with research pharmacists at each clinical site to assure a reliable supply of study creams are shipped to the research pharmacies. It is anticipated that batches will be shipped approximately quarterly. CE cream and its placebo are stable for storage and shipment at room temperature.

Unused cream: Study cream tubes will all be weighed before being dispensed, and study participants will be asked to return their used tubes to the Research Coordinator (upon receipt of their next tube) in order to weigh these spent tubes and calculate total volume/grams cream used. This will be one metric of participant adherence to study medication. Unused cream will be destroyed by the Research Coordinator or the research pharmacist of the Investigative Drug Services pharmacies.

Accountability records: Study participants will be provided a “Medication Calendar” and given instructions for marking the days that they apply their study cream. Subjects will be asked to return their Medication Calendar along with the remaining study cream tube at their follow-up visits. Additional detail is provided in the Manual of Operations & Procedures.

5.3 Concomitant Interventions

5.3.1 Allowed Interventions

- *Medications:* If vaginal discharge is encountered during the setting of study cream use, e.g. vaginal *Candidiasis* or bacterial vaginosis, appropriate treatment may be provided. For simplicity of not having to coordinate application of multiple vaginal creams (e.g., study cream and anti-fungal cream), oral treatments are preferred, e.g. diflucan or metronidazole pills for *Candidiasis* or bacterial vaginosis, respectively.
- *Surgical:* in addition to the required surgical intervention of uterosacral or sacrospinous ligament suspension (see 5.3.2), anterior/ posterior colporrhaphies, vaginal hysterectomy, and midurethral slings are allowed.

5.3.2 Required Interventions

- *Surgical:* All patients will undergo uterosacral ligament suspension (“USLS”) similar to that described by Shull⁷⁶ and a prior network (PFDN) surgical trial⁶⁸ with agreement on number, placement, and type of sutures: 2-3 sutures placed bilaterally (4-6 total) beginning at or above the level of the ischial spine, with 1 delayed absorbable suture caudad and 1 or 2 permanent monofilament suture(s) ~1 cm cephalad. If uterosacral ligaments are deemed unusable due to scarring or inaccessibility—or by surgeon preference—the surgeon may instead perform a unilateral sacrospinous ligament fixation (“SSLF”) in the same fashion described previously⁶⁸ also with 2 permanent and 2 delayed absorbable sutures (4 total). Based on level I evidence, *neither USLS nor SSLF is superior to the other for anatomic, functional, or adverse event outcomes.*⁶⁹ Participating study surgeons must have performed ≥ 20 of each vault suspension procedure with ≥ 5 in the 12 months before subject enrollment.

5.3.3 Prohibited Interventions

- *Medications:* Any oral or transdermal estrogen, Selective Estrogen Receptor Modulator (SERM), or other medication impacting vaginal milieu
- *Surgical:* Any placement of transvaginal mesh for prolapse

5.4 Adherence Assessment

The planned analyses will be according to a *modified intention-to-treat principle (mITT)*: i.e., all participants that are randomized *and* undergo a surgical prolapse repair *and* have at least one postoperative assessment will be analyzed according to their randomized assignment group. All eligible subjects who consent to the study and are enrolled will be available for analysis of baseline characteristics, and those that are randomized and use their study drug will be monitored for adverse events, but they must meet the additional qualifications above (i.e., undergo surgery and have a postoperative assessment) to be analyzed for the primary study outcome.

Various *per-protocol* analyses will also be considered, the first being an analysis similar to the *modified ITT* above but for only those participants receiving the *per-protocol* surgical repair (USLS or SSLF, see 5.3.2). Other *per-protocol* analyses will be comparisons of the

subset of participants in the two randomized groups who are *adherent* to their study medications. Therefore, defining *drug adherent* is critical. This will be defined in three ways: “strict”, “per pivotal study”, and objectively using VMI.

“Strict” Adherence Definition

Drug adherent will be defined as **>80% compliant to expected dosing using the subject’s returned tubes** (i.e., comparing returned tube weights to that expected with at least 80% adherence) and/or **Medication Calendar**. Should there be a discrepancy in adherence designation between tube weight and medication calendar (e.g., using tube weights, the participant appears to have been non-adherent to study protocol but her calendar suggests she was adherent with at least 80% of planned doses recorded as completed), we will defer to the more objective tube weight.

“Per Pivotal Study” Adherence Definition

One of the 3 recommended dosage and administration schedules per Pfizer’s package insert for Premarin® cream is twice-weekly administration of 0.5g intravaginally. This was based on a pivotal study by Bachmann et al in 2009.⁶³ In this study, the twice-weekly CE group of participants was defined as adherent with their drug if they self-reported, on average, at least *once-weekly* (and not more than three times weekly) application of the cream on their paper diary; medication tube weights were not collected. Similarly, in IMPROVE, if participants report via their Medication Calendar that they have applied their cream at least 50% of what is expected, this will be considered adherent.

Alternative Definition: using VMI

Cytomorphologically, vaginal atrophy can be defined by high numbers of (para)basal and intermediate cells and very low numbers of superficial cells. In a prolonged low-estrogen state, superficial cells are no longer produced, leaving essentially only parabasal and basal cells lining the vaginal wall. The Vaginal Maturation Index (VMI) will serve as an important *objective tool* to assess patient adherence with local estrogen application in those participants randomized to vaginal estrogen. This is a quantifiable measure of the proportion of vaginal epithelial superficial cells to parabasal and intermediate cells. While there is not a universally agreed-upon formula to calculate VMI or a cutoff to absolutely define “atrophic” vs. “estrogenized”, several studies point toward the following⁷⁷:

0 x % parabasal cells + 0.5 x % intermediate cells + 1.0 x % superficial cells.

A cutoff of 50 or less is indicative of atrophy.⁷⁸ Therefore, a **score >50 is indicative of study drug adherence in those randomized to active CE cream**.

The ThinPrep® system and its alcohol-based fixative allows for immediate cell fixation after swabbing of the upper vagina with a plastic spatula so the specimen is stable for transport to UT Southwestern for analysis, and the automated system assures greater uniformity and consistency in slide preparation. The VMI assessment will be conducted by a blinded examiner ([name] and/or his trained designee).

The VMI will be collected at Baseline, at time of surgery (or Pre-op clinic visit), and at 12

months postoperatively; if the participant is withdrawing or withdrawn before 12 months postoperatively, a final visit VMI will be collected. While this will provide objective assessment of adherence in those patients randomized to active CE cream, it will not suffice for those randomized to placebo cream (in which case, even adherent patients are expected to demonstrate objective atrophy on VMI) or when participants are unwilling to have VMI collected or if the specimen is deemed uninterpretable by the blinded pathologist.

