Design: Randomized, double-blind, placebo-controlled trial of pre- and postoperative intravaginal estrogen therapy in 222 postmenopausal women with symptomatic prolapse undergoing a standardized surgical repair using native tissue.

Primary outcome: prolapse recurrence as defined by a composite of objective prolapse beyond the hymen, subjective/symptomatic prolapse (feeling of a bulge or *no change* or *worse* on the patient's global impression of improvement), or retreatment (e.g., reoperation or pessary use) assessed 1 year postoperatively. *Time to failure* will be compared in the two groups.

Important secondary outcomes assessing for changes in overactive bladder and urinary incontinence symptoms will be made by comparing symptoms (validated questionnaires) from Baseline to Pre-op/time of surgery. Aim 3 (see above, histomorphology, connective tissue studies) will be assessed from full thickness anterior apical vaginal wall biopsies taken at the time of surgery.

Interventions and Duration

Intervention: 1g conjugated estrogen (CE) cream (Premarin®, Pfizer Inc.) given nightly for 2 weeks then twice-weekly to complete planned 6-8 weeks (5 weeks minimum) therapy before a standardized uterosacral or sacrospinous ligament suspension transvaginal prolapse repair surgery. Those with a uterus will undergo concomitant total vaginal hysterectomy first. Twice-weekly CE cream application is then resumed upon discharge and continued for 1 year postoperatively.

Comparator: placebo vaginal cream, same schedule

Duration: The primary outcome of prolapse recurrence is assessed at one year postoperatively with continued surveillance of participants until 3 years postoperatively.

Sample Size and Population

Total sample size: N=222; 111 per treatment group

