6.2.4 Completion/Final Evaluation

See 36-month Postoperative Visit above.

At the completion of 36 months or at the participant’s final visit (if early withdrawal), “Final Status” documentation (**Form 20**) will be completed. This gives the following possible reasons for withdrawal: ineligible/ screen failure (few, if any, of these are anticipated); subject never began Study Cream; subject did not complete/undergo surgery; subject voluntarily withdrew from study (reason specified); investigator withdrew patient from study (reason specified); lost to follow-up; death; transition to long-term resident or skilled nursing facility; study termination; other (reason specified).

Possible reasons for early withdrawal by the subject may include intolerance of the study medication, patient preference, or inability to continue with follow-up examinations and assessments. Early withdrawal of the participant by the investigator may also be for participant’s inability to adhere to study medication or visits.

If a participant withdraws (or is withdrawn) after randomization but before 12 months postoperatively, there is a prompt to the research coordinator/ physician examiner to collect a final VMI specimen.

It is not anticipated that participants will need to continue to be monitored after study withdrawal and discontinuation of the study medication.

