9.5 Data Analyses

Aim 1. The **primary outcome** will be analyzed according to the assigned treatment group (modified intention-to-treat): i.e., all participants that are randomized *and* undergo a surgical prolapse repair *and* have at least one postoperative assessment will be analyzed according to their randomized assignment group. All eligible subjects who consent to the study and are enrolled will be available for analysis of baseline characteristics, and those that are randomized and use their study drug will be monitored for adverse events, but they must meet the additional qualifications above (i.e., undergo surgery and have a postoperative assessment) to be analyzed for the primary study outcome. At baseline, continuous measures will be compared between groups with Student's t-test and chi-square (or Fisher's exact test) for categorical measures. Scores from repeated surveys are continuous outcomes data and will be analyzed using repeated measures analysis of variance. We will test for interactions between time effect and treatment effect. For categorical data (e.g. prolapse stage), the analysis will be by categorical data modeling using weighted least squares and mixed logit models, with cross-sectional assessments (at specific time intervals) by chi-square. For missing follow-up points there are two possible approaches: (i) if there are few missing follow-up points, then their values may be imputed through multiple imputation methods, in which case repeated measures analysis of variance may be used following multiple imputation; (ii) more likely, we will make time a random effect and a mixed effects model with repeated measures will be applied. Time-to-event or event-free-time will be analyzed using survival methods to include the log-rank test and Cox regression. For measures that may not be assumed normal, the data will be transformed using a rank transformation prior to analysis.

In accordance with NIH policy, we will include an analysis of the intervention effect (CE cream) performed by racial/ethnic subgroups, recognizing that the analyses will not have high statistical power for detecting clinically meaningful differences between races/ethnicities.

Aim 2 Outcomes. As above, continuous scores from repeated surveys will be analyzed using repeated measures analysis of variance with appropriate corrections made, as necessary, for missing data.

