Subaim 2a & 2b. Assuming a baseline UDI-6 score (*obtained from the PFDI-20*) of 7.90 ± 1.91 for the stress-incontinent subpopulation of IMPROVE (expected to be at least 60%, or 67 participants per study arm)¹⁰⁵, in order to demonstrate a clinically meaningful improvement (decrease) of $0.5(\text{SD})^{106}$ to 6.95 ± 1.91 using CE cream from baseline to time of surgery (preop), with 80% power and $\alpha 0.05$, 65 participants are needed per arm. Further, to demonstrate an improvement in a baseline IIQ-7 score (*obtained from the PFIQ-7*) of 9.67 ± 7.14^{105} to 6.12 ± 7.1 , 64 participants are needed per arm (Subaim 2a). Similarly, to find a clinically important improvement (increase) in overall PISQ-12 score from baseline 25.0 ± 4.95 (women with prolapse¹⁰⁷) to 27.48 ± 4.95 at preop (or any postoperative time point), 64 participants are needed per arm (Subaim 2b). Thus, enrollment goals designed to address the primary aim (Aim 1) are sufficient to address these important secondary aims.

Because midurethral slings and anticholinergic or beta-3 agonist medications are not excluded in study participants, these other interventions will clearly impact upon

incontinence rates and will be controlled for in statistical comparisons between the two groups. Gross estimates of overactive bladder in the 2 groups will also be assessed by rates of anticholinergic or beta agonist use, as medication history will be queried at each patient encounter. Modest improvements in *stress* and overall urinary incontinence will be assessed from baseline to Pre-op (i.e. approximately 6-8wks local estrogen) using the relevant PFDI-20 and PFIQ-7 questions (see above Analyses) at both time points.

Subaim 2c. Proportions of participants with postoperative cystitis will be compared using chi-square. Using the liberal definition of post-operative cystitis to include any patient prescribed antibiotics for cystitis symptoms, this study will have sufficient power to demonstrate an improvement from a 22% cystitis rate to 10% (80% power, α 0.05). The postoperative “MedSurg” history form (**Form 15**) queries whether there has been any interval occurrence of urinary tract infection (Item B4) and whether symptoms were treated empirically (i.e., no urine culture) or if culture-proven.

Subaim 2d. Comparisons of vaginal maturation index and atrophy symptoms will use analysis of covariance, with treatment and study center as factors and baseline values as the covariate.

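### The analysis set for the Baseline-to-Pre-op symptom comparison is not clearly defined; read literally, section 5.4 makes it depend on later surgery and follow-up, and the stated 67 per arm allows for no loss before surgery

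*Combined protocol and SAP*

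**What the plan says.** **Analysis set.** Section 5.4 opens: "The planned analyses will be according to a *modified intention-to-treat principle (mITT". The set is randomised women who have a prolapse repair and at least one postoperative assessment, analysed as assigned. The next sentence makes all enrolled women available for baseline characteristics, and has those who are randomised and use the cream monitored for adverse events. It then says women must meet the extra conditions ("i.e., undergo surgery and have a postoperative assessment) to be analyzed for the primary study outcome"). Section 9.5, under Aim 1, says the "primary outcome will be analyzed according to the assigned treatment group (modified intention-to-treat" set applies. The Aim 2 paragraph of 9.5 refers back to the methods above it and says "continuous scores from repeated surveys will be analyzed using repeated measures analysis of variance with appropriate corrections made, as necessary, for missing data". It names no set.

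**The outcome.** The Précis lists among the important secondary outcomes an assessment of "changes in overactive bladder and urinary incontinence symptoms will be made by comparing symptoms (validated questionnaires) from Baseline to Pre-op/time of surgery". Section 9.5 sizes Subaim 2a on this change in the stress-incontinent subgroup, "expected to be at least 60%, or 67 participants per study arm", and states that 65 per arm are needed. It also allows the Subaim 2b score to be compared at Pre-op. Section 9.4.2 collects the Subaim 2d atrophy symptoms at Pre-op among other times.

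**Data on leaving.** The Pre-op visit (6.2.3 and Table 1) is timed only as within two weeks of surgery. Section 6.2.4 has Form 20 completed at an early exit, with not undergoing surgery as its own reason, separate from voluntary withdrawal. For exits before 12 months, "there is a prompt to the research coordinator/ physician examiner to collect a final VMI specimen". It does not name the questionnaires (Form 10), and it does not expect monitoring after withdrawal. Section 8, by contrast, asks women who withdraw voluntarily to keep attending scheduled evaluations and to complete an end-of-study evaluation.

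**The concern.** The Baseline-to-Pre-op change is complete before the operation. Whether a woman is later operated on and seen afterwards should not decide whether she counts in that comparison. Both are post-randomisation events. Surgery is elective and chosen for symptomatic prolapse, and 6.2.4 itself names intolerance of the study medication as a possible reason for leaving. If the cream changes symptoms, tolerability or the decision to go ahead, then being in the set could depend on both arm and outcome, and the randomised comparison would no longer be protected.

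There is also a reproducibility problem. One statistician could follow the opening sentence of 5.4 and another could confine mITT to the primary outcome, as its next sentence and 9.5 suggest. They would report different denominators for the same endpoint, and the choice could be made after the data are seen.

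Finally, the sample-size text and the literal rule do not fit together: 67 per arm counts women whom the opening sentence of 5.4 would exclude.

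**Working it through.** **Inputs.** 222 randomised, 111 per arm (Précis). Loss before surgery 15% (9.2) or 10% (9.5, Aim 3). UDI-6 mean 7.90 falling to 6.95, SD 1.91, 80% power, alpha 0.05, at least 60% stress-incontinent, 65 per arm needed (9.5, Subaim 2a). Two-sided alpha is assumed, because 9.5 does not say; the one-sided calculation gives 50 per arm and does not match.

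**1. Reproduce the stated 65.**
- Standardised difference: (7.90 − 6.95)/1.91 = 0.95/1.91 = 0.497.
- Normal approximation: n per arm = 2 × (1.960 + 0.842)² × (1.91/0.95)² ≈ 63.5, so 64.
- Two-sample t-test: 64.4, so 65. The plan's figure reproduces.

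**2. Where 67 comes from.** 0.60 × 111 = 66.6, rounded to 67. This is 60% of everyone randomised. The same plan derives its total of 222 from 188 by allowing 15% loss before surgery (188/0.85 = 221.2, rounded up), but takes none of that loss off the 67.

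**3. Apply the plan's own loss, equal in both arms (assumption).**

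| Loss before surgery | Stress-incontinent women per arm | Power (t-test, difference 0.95, SD 1.91) |
|---|---|---|
| None | 67 | 81.5% |
| 10% | 67 × 0.90 = 60.3 | 77% |
| 15% | 67 × 0.85 = 57.0 | 75% |

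Both reduced figures are below 65. Excluding women who were operated on but never seen afterwards would lower them further.

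**4. What 65 would take.**
- At 60% prevalence and 10% loss: 65/(0.60 × 0.90) = 120.4, so 121 randomised per arm.
- At 60% prevalence and 15% loss: 65/(0.60 × 0.85) = 127.5, so 128 per arm. The plan has 111.
- Keeping 111 per arm, prevalence would have to be 65/(111 × 0.90) = 65% or 65/(111 × 0.85) = 69%.

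**5. Data capture, side by side.** Section 8 covers voluntary withdrawal and asks for an end-of-study evaluation without listing its contents. Section 6.2.4 covers every early exit, including not having surgery, and names only Form 20 and the VMI specimen. It refers the final evaluation to the 36-month visit, which does include Form 10, but does not say that this content applies to a woman leaving before surgery. A woman who cancels before her Pre-op visit has no surgery date from which to time that visit.

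**The case against.** A reader might infer that women who cancel surgery are definitely dropped from Subaim 2a. The documents do not establish that. The second sentence of 5.4 and the Aim 1 text of 9.5 attach the surgery requirement to the primary outcome, and a figure of 67 based on all randomised women may itself show that Aim 2 was never meant to be restricted. This stands: the finding is an undefined set with one literal reading that excludes them, not a stated exclusion.

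A reader might also infer that nobody asks these women for questionnaires. Section 8 rules that out for voluntary withdrawal. What remains is a mismatch between sections 8 and 6.2.4, most visible for women recorded as not having surgery.

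Nor is bias shown. No text says the cream changes uptake of surgery. In the pilot (2.2a) two women per group had no operation, for reasons unrelated to study medication. That is small but points the other way, and the size of any bias cannot be computed from the documents.

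On magnitude, three cautions stand. Sixty per cent is given as a minimum. The planned repeated-measures or mixed model need not have the power of an unadjusted t-test. And a woman with no Pre-op score adds no Pre-op observation under any set, so naming the right set does not by itself restore 67. None of these answers the missing definition, or the absence of any deduction for loss in the 67.

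**Conclusion.** The point holds as a gap in definition with a measurable consequence for the stated power. The plan should name the set for the Baseline-to-Pre-op comparison (Subaim 2a and the Pre-op parts of 2b and 2d). If the opening sentence of 5.4 were followed literally, that comparison would be conditioned on later events and could be biased; the direction and size are unknown.

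On the plan's own loss figures, about 60 or 57 stress-incontinent women per arm would remain against 65 needed, with power of about 77% or 75% instead of 81.5%. This assumes 60% prevalence, equal loss by arm, two-sided alpha 0.05 and a two-sample t-test. The statement in 9.5 that enrolment for Aim 1 suffices for Subaim 2a is therefore not supported at 60% prevalence if women lost before surgery contribute no Pre-op data.

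This should be corrected, but it concerns an important secondary outcome. It is not a criticism of the primary analysis.

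**What to change.** 1. **Sections 5.4 and 9.5.** State that mITT applies to postoperative outcomes. State that Baseline-to-Pre-op outcomes (Subaim 2a, and the Pre-op parts of 2b and 2d) are analysed in all randomised women by assigned arm, with missing Pre-op scores handled by the mixed model or multiple imputation already described in 9.5. Do not define the set as women who happen to have a questionnaire, since that again selects on a post-randomisation event.
2. **Sections 6.2.4 and 8.** Add Form 10 to the early-exit prompt for women who leave before surgery, whatever the reason recorded on Form 20. Record its date relative to the start of cream, because an exit score may not reflect the planned 6–8 weeks of use. Reconcile the two sections on what is collected after withdrawal.
3. **Section 9.5, Subaim 2a.** Restate the available number and power after expected loss before surgery, using one loss rate or showing both 10% and 15%.

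The cost is a few sentences of text and one existing questionnaire at an exit contact where a VMI specimen is already requested. The downsides are different denominators for pre- and postoperative outcomes, which need a line in the tables, and a slightly less favourable stated power.
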